7.2. Statistical Methods

Given the exploratory nature, descriptive statistics and graphic visualizations will be provided. No formal statistical hypothesis testing is anticipated.

7.3. Statistical Analyses

7.3.1. Pharmacokinetic Analysis

7.3.1.1. Pharmacokinetic Parameters

To assess the pharmacokinetics of DMT/harmine dose formulations, the PK parameters detailed in Section 5.3 will be listed and summarized for subjects in the PK analysis sets (as defined in Section 4.2 and Section 4.4.1). Missing values will be handled as detailed in Section 6. Each PK parameter will be summarized by dose combination, and will include the set of summary statistics as specified in the table below:

Table 1. PK Parameters to be Summarized Descriptively

Parameter	Summary Statistics
AUC, Cmax	N, arithmetic mean, median, cv%, standard deviation, minimum, maximum, geometric mean and geometric cv%.
T $\frac{1}{2}$	N, median, minimum, maximum.

There will be 1 summary table presenting all PK parameters. This will include data from all dose combinations. The treatment subheading will include the dose condition and dosing regimen information.

To assess the relationship between the PK parameters and dose, dose normalized AUC and Cmax will be plotted against dose.

If the conditions listed in Section 3.2 are met, AUC (if data permit) and Cmax will be analyzed using mixed-effects models for all administered dose combinations. The purpose of these analyses is to obtain estimates of the intra-subject variation to assist in the planning of future studies.

Supporting data from the estimation of 'T $\frac{1}{2}$ ' will be listed by analyte where applicable: terminal phase rate constant (k_{el}); goodness of fit statistic from the log-linear regression (r^2); the percent of AUC based on extrapolation, and the first, last, and number of time points used in the estimation of k_{el} . This data may be included in the clinical study report.

Presentations for DMT and harmine concentrations will include:

- concentration data according to dose conditions, number of doses administered, and nominal time points for individual subjects in the form of a table of concentration data organised to present the effect of dose parameters and time for individuals. Conventional summary statistics for concentration data above the lower limit of quantification will accompany these results.
- plots of median concentrations against nominal time post-dose by dose combination.
- boxplots of dose-normalized AUC and Cmax for each dose combination and number of administered doses per dose combination.
- plots of mean concentrations against nominal time post-dose by dose combination.
- plots of individual concentration against actual time post-dose by dose combination.
- plots of individual concentration by subject against actual time post-dose.

For summary statistics, median and mean plots by sampling time, the nominal PK sampling time will be used, for individual subject plots by time, the actual PK sampling time will be used.

7.4. Safety Analysis

For each dose combination a set of summary tables split by treatment will be produced separately to evaluate the safety/tolerability of each DMT/harmine dose combination.

No formal analyses are planned for safety/tolerability-related data. The other endpoints detailed in Section 5 will be listed and summarized in accordance with sponsor reporting standards, where the resulting data presentations will consist of subjects from the safety analysis set.

7.4.1. Treatment and Disposition of Subjects

Subject evaluation groups will show end of study subject disposition and will show which subjects were analyzed for pharmacokinetics, as well as for safety (adverse events and laboratory data). Frequency counts will be supplied for subject discontinuation(s) by treatment.

Data will be reported in accordance with the sponsor reporting standards.

7.4.2. Demographic and Clinical Examination Data

A breakdown of demographic data will be provided for age, race, weight, body mass index and height. Each will be summarized by cohort and overall in accordance with the sponsor reporting standards.

7.4.3. Subject Discontinuation(s)

Subject discontinuations refer to the complete cessation of participation in the study (i.e. dropout), either due to adverse events, personal reasons, or other factors that prevent the participant from attending subsequent dose combination study days. Discontinuations are distinct from declined (intra-visit) dose escalation, where a subject may choose not to receive all dose escalations within a single visit but continues to participate in the study.

Discontinuations due to adverse events, will be thoroughly documented and summarized by treatment group. Data will be reported in accordance with the sponsor reporting standards.

7.4.4. Adverse Events

Adverse events will be reported in accordance with the sponsor reporting standards.

7.4.5. Laboratory Data

Laboratory data will be listed and summarized by treatment in accordance with the sponsor reporting standards.

Mean change from baseline will be plotted against nominal time post dose. On each plot there will be one line for each treatment. Individual plots of changes from baseline will also be produced for each dose combination and total doses per dose combination.

7.4.6. Vital Signs Data

Absolute values and changes from baseline in supine systolic and diastolic blood pressure and pulse rate will be summarized by treatment and time post-dose, according to sponsor reporting standards. Tables will be paged by parameter. Baseline is as defined in Section 5.

Mean changes from baseline for supine systolic and diastolic blood pressure and pulse rate will be plotted against time post-dose. On each plot there will be a separate line for each treatment. Data from all dose conditions will be plotted on the same figure using separate lines for different dose combinations. Corresponding individual plots of changes from baseline will also be produced for each dose combination.

For supine systolic and diastolic blood pressure and pulse rate, the differences between each dose and placebo (dose – placebo) will be summarized (N, mean, 95% confidence interval) and plotted (mean) for each dose combination and timepoint (including baseline).

Maximum absolute values and changes from baseline for vital signs (for supine) will also be summarized descriptively by treatment. Numbers and percentages of subjects meeting the categorical criteria will be provided. All planned and unplanned post-dose timepoints will be counted in these categorical summaries. All values meeting the criteria of potential clinical concern will be listed.

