3.1. Study Design

This is a single-blind, randomized, two-arm, dose-response study of DMT and harmine in healthy subjects.

N = 16 healthy female and male subjects (25-45 y) with no current or previous history of neurological or psychiatric disorder and no first-degree relatives with history of Axis-I psychiatric disorder will be recruited by medical screening. In this open-label pilot study, acute subjective effects and blood samples following the administration of escalating doses of DMT and harmine as a sublingual single preparation are measured. Additionally, on the fourth test day participants will receive either DMT or harmine only as a sublingual preparation according to their arm allocation. The study will be conducted at the Psychiatric University Hospital Zurich (PUK). Study participants will undergo a telephone and medical screening before enrolment to the study. Possible doses for each study day are given in section 3.4. Blood sampling and pharmacokinetic modeling, as well as assessing vital signs and the intensity of subjective effects follows the timeline shown in the figure below. Blood is sampled 15 times over the course of 24 h. Vital signs and the intensity of subjective effects will be monitored throughout the study at baseline, 0, 20, 40, 60, 85, 120, 150, 180, 240, 300, 540, 1440 (= 24h) after administration. This protocol is used for all 6 pilot days. ECG is measured

at baseline, 75, 150, 300, 540, and 1440 min after administration. Body temperature is measured at baseline, 75, 180, 300, 540, and 1440 min after administration. Semistructured interviews will be conducted on the second study day towards the end of the study day. The 'Aliveness' Task will be conducted on the first 3 study days at ~100 min after substance administration. Participants will be released at the end of the study day but will come back the following day for their assessments 24 hours after first substance administration.

The daily schedule for study events are displayed in Figure 3. A detailed description of the schedule for the study participation and procedures is provided in the accompanying protocol (BASEC-Nr. 2022-00973).

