3.1.1. Initial titration period

We will administer the sublingual formulation with varying fixed starting doses of DMT and harmine and let the study participants increase the total dose of DMT and harmine in 20 minute intervals at fixed increments up to two times. We will test 7 different dosing conditions with varying DMT:harmine ratios during the first 4 days (see figure 1). The tested ratios range between 0-120 mg DMT and 0-180 mg harmine. The dose ratios will be administered in a sequential order with two different sequences in two arms, and the DMT or harmine only condition will be tested on the fourth study day; this is done to further clarify if DMT alone is capable of inducing its effects with routes other than intravenous administration or inhalation. The DMT/harmine only condition is the only one that is exclusive for one of the two study arms. The rationale behind this dosing scheme is to find the optimal dose of harmine and DMT independently of each other by taking account for order/PD habituation and linear/non-linear drug-drug-interaction effects and to establish the optimal dosing for the future studies based on PK/PD analytics.

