3.1.2. Non-identical cross-over period

A non-identical cross-over paradigm will be applied on days 5 and 6. This scheme will allow us to explore DMT/harmine in additional combinations which were explored in the initial titration phase so that all individuals in both treatment arms have been exposed to all combinations, except for the DMT-only and Harmine-only conditions which are unique to each arm. The timeline for this study is shown in figure 2.

[figure not shown]

Figure 1. Dose ratios for the dose-finding study. The sublingual formulation is administered in a ratio-varying manner on six study days in two arms that differ in the order of substance administrations (equivalent to a cross-over design). On the 4th study day, participants will either receive DMT or harmine only, depending on the arm they are allocated to.

RE01 - DHTP - Statistical Analysis Plan

[figure not shown]

Figure 2. Study flow chart for the dose-finding study.

[figure not shown]

Figure 3. Timeline of drug administration and assessments for each study day.

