5.1. Primary Endpoint(s)

- Pharmacokinetic parameter "Cmax": Dose-dependent changes in Cmax of several doses of combined DMT & Harmine.
- Pharmacokinetic parameter "Area under the curve (AUC)": Dose-dependent changes in AUC of several doses of combined DMT & Harmine.
- Pharmacokinetic parameter "T1/2": Dose-dependent changes in T1/2 of several doses of combined DMT & Harmine.
- Incidence of Treatment-Emergent Adverse Events: Dose-dependent changes in incidence of adverse drug reactions.
- Blood count (Lab biochemistry): Changes from baseline in blood count.
- Clinical chemistry (Lab biochemistry): Changes from baseline in any clinical chemistry parameter with potential clinical relevance.
- Blood coagulation (Lab biochemistry): Changes from baseline in blood coagulation.
- QT interval (12-lead Electrocardiogram [ECG]): Dose-dependent changes of QT intervals assessed by clinical 12-lead ECG).
- Blood pressure: Dose-dependent changes in systolic and diastolic blood pressure.
- Heart rate: Dose-dependent changes in heart rate.

- Temperature: Dose-dependent changes in body temperature (in °C).
- Genotyping: Collection of saliva-samples to determine genetic polymorphisms.
- Subjective effects: Dose-dependent changes in trajectories of subjective effects.

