7.4.7. ECG Data

Absolute values and changes from baseline in QT, heart rate, QTcF, PR and QRS will be summarized by dose combination and time post-dose using sponsor reporting standards. Tables will be paged by parameter. Baseline is as defined in Section 5.

Mean changes from baseline in QT, heart rate and QTcF will be plotted against time post-dose. On each plot there will be 1 line for each treatment. Data from all dose combinations will be plotted on the same figure using separate lines for different dose combinations. Corresponding individual plots of changes from baseline will also be produced for each dose combination.

Changes from baseline in QTcF will also be plotted separately against drug concentrations. This will be a scatter plot for all observations where QTcF and drug concentration are recorded. Different symbols will be used for each treatment.

Maximum increase from baseline for QTcF, heart rate, QT, PR and QRS will be summarized by dose combination, according to sponsor reporting standards.

In addition, for QTcF, heart rate and QT, the differences between each dose combination (dose combination 1 – dose combination 2) for each subject will be summarized and plotted (N, mean, 95% confidence interval) for dose combination and timepoint (including baseline).

ECG endpoints and changes from baseline (QTcF, PR and QRS) will also be summarized descriptively by dose combination using categories as defined in Section 8.1 (for QTc these correspond to ICH E14¹). Numbers and percentages of subjects meeting the categorical criteria will be provided. All planned and unplanned post-dose timepoints will be counted in these categorical summaries. All values meeting the criteria of potential clinical concern will be listed.

Listings of subjects with any single post-dose value ≥ 500 msec will also be produced for QTcF.

QTcB will be listed only and not summarized.

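### SAP Section 7.4.6 plans dose-minus-placebo differences for blood pressure and pulse rate, but the design has no placebo condition, so the output cannot be computed

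*SAP*

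**What the plan says.** SAP Section 7.4.6 contains a sentence that opens "For supine systolic and diastolic blood pressure and pulse rate, the differences between each dose and placebo". It specifies that "the differences between each dose and placebo (dose – placebo) will be summarized (N, mean, 95% confidence interval") and the mean plotted, by dose combination and timepoint, with baseline counted as a timepoint.

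The design sections describe active dosing only:

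- Section 3.1.1: "We will test 7 different dosing conditions with varying DMT:harmine ratios during the first 4 days".
- Section 3.1: "on the fourth test day participants will receive either DMT or harmine only", according to arm. Of the assessment schedule the same section says "This protocol is used for all 6 pilot days".
- Section 3.1.2: after days 5 and 6, "all individuals in both treatment arms have been exposed to all combinations, except for the DMT-only and Harmine-only conditions". The caption of Figure 1 has the sublingual formulation given on all six study days.

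Section 5.1 lists among the primary endpoints "Blood pressure: Dose-dependent changes in systolic and diastolic blood pressure". Section 7.4.7 plans the corresponding ECG output with a different comparator: "for QTcF, heart rate and QT, the differences between each dose combination", taken per subject and also with N, mean and 95% confidence interval.

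**The concern.** A planned output names a comparator that the design does not provide. Placebo appears nowhere else in the readable text of the SAP.

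The sentence matters because of what it is meant to deliver. The blood pressure endpoint is defined as a dose-dependent change, and the placebo difference is the only comparison between conditions with an interval that the SAP plans for it. The conditional mixed models in Sections 3.2 and 7.3.1.1 cover subjective effects, AUC and Cmax. The contrast in Section 7.4.7 covers QTcF, heart rate and QT. If the sentence stays, the programmer must either drop the output or pick another comparator once the data are in hand, and preventing that choice is one purpose of a SAP.

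**Working it through.** **1. Is there room for a placebo condition?**

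Inputs: 6 study days per subject (Section 3.1, Figure 1 caption); day 4 is a single-drug day (Section 3.1); 7 conditions (Section 3.1.1); both arms receive every combination except the two single-drug conditions (Section 3.1.2).

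- Combination days per subject: 6 - 1 = 5, so there are 5 combinations shared by both arms.
- Distinct conditions: 5 shared + DMT-only + harmine-only = 7. This reproduces the SAP's figure.
- Cross-check on days 1 to 4: 2 arms x 4 days = 8 arm-days. With one combination common to both arms on days 1 to 3, that is 8 - 1 = 7 distinct conditions. Each arm then lacks 5 - 3 = 2 combinations, which days 5 and 6 supply.

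No condition or day remains for placebo. The count alone does not show that all five shared conditions are active; the wording does. Sections 3.1 to 3.1.2 describe them as DMT/harmine combinations with starting doses and increments, and the Figure 1 caption has the formulation given on all six days. The 0 mg ends of the dose ranges in Section 3.1.1 are accounted for by the two single-drug conditions.

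**2. Could placebo mean baseline?** No. Section 7.4.6 plans changes from baseline separately, and the placebo difference is itself to be shown at baseline.

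**3. How much output is affected?** Section 3.1 lists 13 timepoints for vital signs: baseline, 0, 20, 40, 60, 85, 120, 150, 180, 240, 300, 540 and 1440 minutes.

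- All three parameters: 7 x 13 x 3 = 273 rows.
- Systolic and diastolic pressure only: 7 x 13 x 2 = 182 rows.

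These are upper counts of rows that cannot be filled. They do not measure an effect.

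**4. Can a contrast in the style of Section 7.4.7 be computed?** Five shared combinations give 5 x 4 / 2 = 10 within-subject pairs, or 4 contrasts against one named reference. The 95% half-width of a paired mean difference, in units of the SD of the difference, is t(0.975, N - 1) / sqrt(N). N = 16 and N = 12 come from Section 7.1; N = 8 is one arm, assuming equal arms, and applies to contrasts with a single-drug day.

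| N | t / sqrt(N) | Half-width (SD of difference) |
|---|---|---|
| 16 | 2.131 / 4 | 0.533 |
| 12 | 2.201 / 3.464 | 0.635 |
| 8 | 2.365 / 2.828 | 0.836 |

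The SAP gives no SD for blood pressure. Assuming a within-subject SD of 6, 8 or 10 mmHg, and SD of the difference = 1.41 x that SD:

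| N | SD 6 | SD 8 | SD 10 |
|---|---|---|---|
| 16 | ±4.5 mmHg | ±6.0 mmHg | ±7.5 mmHg |
| 12 | ±5.4 mmHg | ±7.2 mmHg | ±9.0 mmHg |

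**The case against.** The best defence is that little depends on this output. Section 7.4 plans no formal safety analysis, Section 7.2 is descriptive throughout, and no decision rule or sample size uses the interval. Section 5.1 lists thirteen primary endpoints, so the label carries less weight than usual. Blood pressure is still summarised by absolute values, changes from baseline, maxima, categories and plots showing all dose combinations together. An output that visibly cannot be run also cannot mislead. This stands as a limit on the harm. It does not make the sentence correct, because a descriptive interval is still a specified output and must be computable.

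A second objection is that some sections are redacted and Figure 1 is not reproduced in the text examined, so a placebo might be described there. The conflict, however, is between Section 7.4.6 and the SAP's own unredacted design text. If a placebo day did exist, Sections 3.1 to 3.1.2 would be the part needing correction.

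A third is that replacing the comparator is a choice, since deletion would also remove the contradiction. All pairs would give 10 x 13 x 3 = 390 intervals. Subjects may decline increments, so pairs matched on total dose could be fewer than 12 to 16, and the fixed sequences may carry day effects. These cautions are fair, but they apply equally to the ECG contrast already planned in Section 7.4.7 and do not rule out a descriptive summary.

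**Conclusion.** The concern holds. The dose-minus-placebo output in Section 7.4.6 cannot be produced, because its comparator has no observations at any timepoint. The loss is confined to the between-condition estimate with an interval for blood pressure and for pulse rate measured as a vital sign. ECG heart rate keeps such an interval through Section 7.4.7, and the rest of Section 7.4.6 needs no placebo. It should be corrected because blood pressure is a primary endpoint defined by dose dependence and has no other planned interval.

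The conclusion rests on the SAP's readable design text. The mmHg half-widths rest on assumed SDs and on complete pairs, and they describe the precision of the replacement, not the size of the error.

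**What to change.** Replace the placebo sentence in Section 7.4.6 with wording such as: within-subject differences between dose combinations in supine systolic pressure, diastolic pressure and pulse rate will be summarised (N, mean, 95% confidence interval) and plotted by timepoint, as in Section 7.4.7, using the combinations given to both arms; the study has no placebo reference. Naming one reference combination would keep the output to 4 x 13 x 3 = 156 intervals in place of 390.

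The cost is one sentence and no added measurements. The downside is that the output supports statements about differences between dose combinations and none about differences from placebo. If the sponsor does not want the contrast, deleting the sentence also removes the contradiction, but leaves blood pressure without an interval comparison.

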7.4.7. ECG Data

Absolute values and changes from baseline in QT, heart rate, QTcF, PR and QRS will be summarized by dose combination and time post-dose using sponsor reporting standards. Tables will be paged by parameter. Baseline is as defined in Section 5.

Mean changes from baseline in QT, heart rate and QTcF will be plotted against time post-dose. On each plot there will be 1 line for each treatment. Data from all dose combinations will be plotted on the same figure using separate lines for different dose combinations. Corresponding individual plots of changes from baseline will also be produced for each dose combination.

Changes from baseline in QTcF will also be plotted separately against drug concentrations. This will be a scatter plot for all observations where QTcF and drug concentration are recorded. Different symbols will be used for each treatment.

Maximum increase from baseline for QTcF, heart rate, QT, PR and QRS will be summarized by dose combination, according to sponsor reporting standards.

In addition, for QTcF, heart rate and QT, the differences between each dose combination (dose combination 1 – dose combination 2) for each subject will be summarized and plotted (N, mean, 95% confidence interval) for dose combination and timepoint (including baseline).

ECG endpoints and changes from baseline (QTcF, PR and QRS) will also be summarized descriptively by dose combination using categories as defined in Section 8.1 (for QTc these correspond to ICH E14¹). Numbers and percentages of subjects meeting the categorical criteria will be provided. All planned and unplanned post-dose timepoints will be counted in these categorical summaries. All values meeting the criteria of potential clinical concern will be listed.

Listings of subjects with any single post-dose value ≥ 500 msec will also be produced for QTcF.

QTcB will be listed only and not summarized.

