5. ENDPOINTS AND COVARIATES

Subjects who receive at least one dose of randomized study IMP and have a baseline and at least one post-baseline measurement (after taking randomized study medication) will be included in the data analyses. Baseline is defined as the last pre-dose measurement from each measurement day.

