5.4.4. ECG

ECGs will be recorded at multiple timepoints throughout the acute measurement period, starting from the pre-dose baseline of each study visit when doses are administered, as detailed in Section 3.3 of the protocol.

The QT, QTc, PR, RR, QRS and heart rate will be recorded at each assessment time.

If not supplied, QTcF will be derived using Fridericia's heart rate correction formula:

$$QTcF = QT / (RR)^{1/3} \quad \text{where } RR = 60/\text{HR} \text{ (if not provided)}$$

If not supplied, QTcB will be derived using Bazett's heart rate correction formula:

$$QTcB = QT / (RR)^{1/2} \quad \text{where } RR = 60/\text{HR} \text{ (if not provided)}$$

The maximum absolute value (post-dose) and the maximum increase from baseline for QTcF, QT, heart rate, PR and QRS, will be determined over all measurements taken post-dose for QTcF, PR and QRS.

The maximum increase from baseline will be calculated by first subtracting the baseline value from each post-dose measurement to give the change from baseline. The maximum of these values over

the respective period will then be selected, except in the case where a subject does not show an increase. In such an instance, the minimum decrease should be taken.

5.5. [REDACTED]

CCI

5.5.1. [REDACTED]

5.5.2. [REDACTED]

5.5.3. [REDACTED]

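### SAP 7.4.7: the within-subject differences between dose combinations in QTcF, heart rate and QT read as differences of absolute values and should be adjusted for the same-day pre-dose value

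*SAP*

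**What the plan says.** SAP 7.4.7 plans, "for QTcF, heart rate and QT, the differences between each dose combination (dose combination 1 – dose combination 2"), a per-subject contrast that "for each subject will be summarized and plotted (N, mean, 95% confidence interval) for dose combination and timepoint (including baseline"). The sentence does not state the scale and does not mention change from baseline.

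The pre-dose value is available on the same day. SAP 5 states: "Baseline is defined as the last pre-dose measurement from each measurement day". SAP 5.4.4 has ECGs recorded "starting from the pre-dose baseline of each study visit when doses are administered", and SAP 3.1 lists ECG times "at baseline, 75, 150, 300, 540, and 1440 min after administration", which is one pre-dose and five post-dose readings per study day.

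Elsewhere in 7.4.7 the pre-dose value is used: "Absolute values and changes from baseline in QT, heart rate, QTcF, PR and QRS will be summarized by dose combination and time post-dose". Mean and individual change plots and maximum increases are planned as well.

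On order, SAP 3.1.1 states: "The dose ratios will be administered in a sequential order with two different sequences in two arms". The Figure 1 caption in 3.1.2 describes "two arms that differ in the order of substance administrations". The DMT-only and harmine-only conditions are given on the fourth study day, each in one arm only.

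**The concern.** If the contrast were a change from baseline, its value at baseline would be zero for every subject, and there would be nothing to summarise there. Absolute values are therefore the natural reading.

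On that scale the contrast removes stable differences between subjects but not differences between study days. Within an arm each combination belongs to one study day. If pre-dose heart rate or QTcF differs systematically between two days, for example through arousal at the first visit, that arm's dose contrast contains the whole of that difference.

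QT interval and heart rate are listed among the primary endpoints in SAP 5.1 as dose-dependent changes, and the primary objective is safety and tolerability. This contrast is the planned interval estimate that compares one dose combination with another on the ECG parameters.

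**Working it through.** **The plan's own figure.** SAP 7.1 gives 12 + 4 = 16 subjects, which reproduces. It gives no standard deviation, correlation or interval width for ECG differences, so those below are assumptions.

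**Inputs.** Six study days less the single-drug day leave 6 − 1 = 5 combinations shared by all subjects (also 7 conditions − 2 single-drug conditions = 5). Let r be the within-subject correlation, across days, between pre-dose and post-dose values, with range 0.3 to 0.7. Let s² be the within-subject variance of one reading.

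**Systematic shift.** Write s_d for the systematic level on day d. If combinations A and B fall on days i and j in one arm and on days k and l in the other, and the arms are equal in size, the bias of the pooled raw contrast is ½[(s_i − s_j) + (s_k − s_l)]. It vanishes if the second sequence mirrors the first for that pair, and otherwise only in part. A contrast involving a single-drug condition rests on one arm, so nothing offsets it. That condition is also tied to day 4, so a study-day term cannot separate the two.

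Share of a shift that remains in an arm's contrast when the shift affects pre-dose and post-dose readings equally:
- raw difference: 100%
- covariate-adjusted, slope about r for equal variances: 1 − r
- difference in change from baseline: 0%

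For an assumed 5 ms shift this gives 5.0 ms raw, (1 − r) × 5 = 3.5, 2.5 or 1.5 ms adjusted, and 0 ms on the change scale. Simulation gave 5.0 ms raw and 0.0 ms on the change scale.

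**Random shift.** With no systematic effect, simulated coverage of the raw 95% interval was 94.9% (n = 12, 20,000 runs). Random day variation widens the interval but does not bias it.

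**Precision.** The variance of a raw difference is 2s², of a difference in changes 4s²(1 − r), and of an adjusted difference about 2s²(1 − r²). The simulated standard errors are in units of s, with 16 subjects, 5 combinations, one pooled slope and 3,000 runs.

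| r | SE raw | SE adjusted | Reduction | √(1 − r²) | Shift kept, simulated | Change/raw width, √(2(1 − r)) |
|---|---|---|---|---|---|---|
| 0.3 | 0.355 | 0.342 | 1 − 0.342/0.355 = 4% | 0.95 | 69% | 1.18 |
| 0.5 | 0.347 | 0.303 | 1 − 0.303/0.347 = 13% | 0.87 | 50% | 1.00 |
| 0.7 | 0.354 | 0.262 | 1 − 0.262/0.354 = 26% | 0.71 | 29% | 0.77 |

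A second simulation with 12 subjects gave 0.414 to 0.400, 0.404 to 0.355 and 0.399 to 0.296, which are reductions of 3%, 12% and 26%.

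**In milliseconds.** With an assumed within-subject QTcF standard deviation of 10 ms and n = 12, the raw half-width is 2.201 × 10 × √(2/12) = 9.0 ms (7.2 to 10.8 ms for a standard deviation of 8 to 12 ms). On the change scale it is 10.6, 9.0 or 7.0 ms for r = 0.3, 0.5 or 0.7.

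**Why one pooled slope.** A slope fitted separately for each pair gives interval widths relative to raw of 1.02 (r = 0.3), 0.92 (0.5) and 0.76 (0.7) at n = 12, and 1.08, 0.98 and 0.81 at n = 8. At low r it loses precision.

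**The case against.** The strongest case against has five parts.

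- **Baseline-corrected results are already planned.** Changes from baseline are summarised and plotted by combination, and the raw difference at baseline is shown beside the later ones, so a reader can see a shift. This stands and lowers the stakes. It does not give a corrected interval for a dose contrast.
- **The stakes are low.** SAP 7.4 plans no formal safety analysis, and no decision rule uses these intervals. This stands.
- **A reader might infer that the intervals are simply wider than needed.** The SAP does not support that. Taking within-subject differences already removes the subject effect, and the gain depends on a correlation that is not given. It is only about 4% at r = 0.3, and subtracting baseline widens the interval whenever r is below 0.5.
- **A reader might infer that all day-to-day variation turns into apparent dose effects.** It does not. Random shifts are noise, and the two sequences partly offset systematic ones. How far depends on Figure 1, which is not shown in the text at hand.
- **A reader might take these for the only heart-rate intervals in the plan.** SAP 7.4.6 also plans 95% intervals for pulse rate, against placebo. No placebo condition appears in the design described in SAP 3.1, so that contrast does not replace the one here, but the claim of uniqueness would be wrong.

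It is also fair to say that covariate adjustment does not cure a systematic shift. It leaves a share of 1 − r. That is why the change-from-baseline difference belongs beside it.

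**Conclusion.** The point holds in a limited form. The paired ECG contrast has no stated baseline correction and reads as a difference of absolute values. That scale is an inference from the inclusion of baseline, because the SAP never names it. A systematic pre-dose difference between days then enters an arm's contrast in full and is offset by the second sequence only in part. It is not offset at all for the single-drug conditions.

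Adjustment with one pooled slope lowers the standard error by about 4%, 13% or 26% and retains about 70%, 50% or 30% of a systematic shift, for an assumed r of 0.3, 0.5 or 0.7. These figures assume equal variances before and after dosing and across combinations, and a shift that acts equally on both readings. Because the intervals are descriptive, the effect on the trial's conclusions is modest. The documents do not show that the planned intervals are invalid or that such a shift will occur.

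**What to change.** In SAP 7.4.7, state the scale of the pairwise differences and make three changes.

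1. **Main presentation.** For each parameter and post-dose timepoint (3 × 5 = 15 fits), use one linear mixed model for the post-dose value. Include dose combination, the same-day pre-dose value as a deviation from the subject's mean pre-dose value with one pooled slope, random subject, and study day where it is estimable. Report pairwise differences with 95% confidence intervals. Note that day 4 cannot be separated from the single-drug conditions.
2. **Comparability check.** Keep the raw difference between combinations at baseline.
3. **Sensitivity analysis.** Show the pairwise difference in change from baseline. It removes an additive shift in full but widens the interval when r is below 0.5.

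The cost is SAP wording and slightly more programming. No new data are needed.
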